## 2.2. SAES

Table 199: SAEs

Adverse Event (CTC)	N (%)
---------------------	-------

Table 200: List of all SAEs with details

## 2.3. TOXICITIES

### 2.3.1. MOST FREQUENT TOXICITIES (RELATED TO ANY TREAT.)

Table 201: Most frequent toxicities (at least 3 pts approx.  $\geq 10\%$ )

	N	%	LL IC 95%	UL IC 95%
No				
Sí				
Total				
No				
Sí				
Total				

Table 202: Most frequent toxicities (at least 3 pts approx.  $\geq 10\%$ ) according to grade

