#### **1.4.2. Durvalumab + tremelimumab**

The safety of durvalumab + tremelimumab combination therapy is being evaluated in the ongoing dose escalation and dose expansion Study 006, in patients with NSCLC, and has so far shown a manageable safety and tolerability profile.

The potential risks with the combination of durvalumab + tremelimumab are similar to those for durvalumab and tremelimumab monotherapy. Emerging data from study 006 and from combinations of other agents in the same class indicate an increased frequency and/or severity of some of these potential immune-mediated toxicities.

In durvalumab+tremelimumab combination studies at the dose of durvalumab 20 mg/kg and tremelimumab 1 mg/kg AEs (all grades) reported very commonly ( $\geq 10\%$  of patients) are fatigue, diarrhoea, nausea, dyspnea, decreased appetite, pruritus, vomiting, anaemia, constipation, cough, abdominal pain, pyrexia, back pain, hyponatremia and rash.

Approximately 13% of patients experienced an AE that resulted in permanent discontinuation of study drug and approximately 13% of patients experienced an SAE

that was related to durvalumab and tremelimumab by the study investigator (Scott Antonia, Sarah B 2016).

A detailed summary of durvalumab + tremelimumab combination AE data can be found in the current version of the durvalumab IB.

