### **10.1.2. Definition of serious adverse events**

A serious adverse event is an AE occurring during any study phase (i.e., screening, run-in, treatment, wash-out, follow-up), at any dose of the study drugs that fulfils one or more of the following criteria:

- Results in death
- Is immediately life-threatening
- Requires in-patient hospitalization or prolongation of existing hospitalization
- Results in persistent or significant disability or incapacity
- Is a congenital abnormality or birth defect in offspring of the patient
- Is an important medical event that may jeopardize the patient or may require medical intervention to prevent one of the outcomes listed above.

The causality of SAEs (their relationship to all study treatment/procedures) will be assessed by the investigator(s) and communicated to the sponsor.

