#### 11.2.2. Efficacy analyses and exploratory analyses

Table 8. *Efficacy analyses and exploratory analyses*

Objectives	Variable	Analysis	Clinical factors	Analysis population
Primary: efficacy of durvalumab plus tremelimumab with concurrent radiotherapy in terms of pathological response rate	Pathological response rate	1. Proportion estimation with a 95% confidence interval 2. Simon two stage decision rule 3. Logistic regression with clinical factors	Tumour size Tumour localization Histology Biomarkers	Per protocol
Secondary 1a: bladder preservation.	Rate of bladder preserved	1. Proportion estimation with a 95% confidence interval 2. Logistic regression with clinical factors	Tumour size Tumour localization Histology Biomarkers	Per protocol
Secondary 1b: bladder preservation.	Rate of immediate and late salvage cystectomies.	1. Proportion estimation with a 95% confidence interval 2. Logistic regression with clinical factors	Tumour size Tumour localization Histology Biomarkers	Per protocol

Secondary 1c: bladder preservation.	Time from start of immunotherapy to the date of recurrence of muscle invasive bladder carcinoma or metastases.	Kaplan Meier estimation of survival with a 95 % confidence interval	Not applicable	Per protocol
Secondary 1d: Overall survival	Time from treatment start to exitus.	Kaplan Meier estimation of survival with a 95 % confidence interval		Per protocol
Secondary 1.3: Progression free survival	Time from treatment start to tumour relapse or distant progression.	Kaplan Meier estimation of survival with a 95 % confidence interval		Per protocol
Secondary 2: Safety profile and tolerability of combination	CTCAE V4.03	1. Frequency table with adverse events, grades and relationship to study drugs and to radiotherapy treatment 2. Frequency table with severe toxicity.	Durvalumab cumulative dose, tremelimumab cumulative dose, radiotherapy treatment constraints (dose in risk organs).	Safety population
Secondary 3: To evaluate the long term functionalism and late sequel of the treatment in the preserved bladders.	Bladder control scale	Repeated measures analysis		Per protocol
Exploratory 1: Biomarkers and pathological response rate	Biomarkers and pathological response rate	Logistic regression in which response or not is the response and baseline biomarkers are factors to be studied	Biomarkers	Per protocol

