## Specific Immune-Mediated Reactions

Adverse Events	Severity Grade of the Event (NCI CTCAE version 4.03)	Dose Modifications	Toxicity Management
Pneumonitis/ Interstitial Lung Disease (ILD)	Any Grade	General Guidance	For Any Grade:
			
 
- Monitor patients for signs and symptoms of pneumonitis or ILD (new onset or worsening shortness of breath or cough). Patients should be evaluated with imaging and pulmonary function tests, including other diagnostic procedures as described below.
 
- Initial work-up may include clinical evaluation, monitoring of oxygenation via pulse oximetry (resting and exertion), laboratory work-up, and high- resolution CT scan.
 

	Grade 1 (asymptomatic, clinical or diagnostic observations only; intervention not indicated)	No dose modifications required. However, consider holding study drug/study regimen dose as clinically appropriate and during diagnostic work-up for other etiologies.	For Grade 1 (radiographic changes only): 
 
- Monitor and closely follow up in 2 to 4 days for clinical symptoms, pulse oximetry (resting and exertion), and laboratory work-up and then as clinically indicated.
 
- Consider Pulmonary and Infectious Disease consults.
 

	Grade 2 (symptomatic; medical intervention indicated; limiting instrumental ADL)	Hold study drug/study regimen dose until Grade 2 resolution to Grade $\leq 1$ . 
 
• If toxicity worsens, then treat as Grade 3 or Grade 4.
 
• If toxicity improves to Grade <math>\leq 1</math>, then the decision to reinitiate study drug/study regimen will be based upon treating physician's clinical judgment and after completion of steroid taper.
 
	For Grade 2 (mild to moderate new symptoms): 
 
- Monitor symptoms daily and consider hospitalization.
 
- Promptly start systemic steroids (e.g., prednisone 1 to 2 mg/kg/day PO or IV equivalent).
 
- Reimage as clinically indicated.
 
- If no improvement within 3 to 5 days, additional workup should be considered and prompt treatment with IV methylprednisolone 2 to 4 mg/kg/day started
 
- If still no improvement within 3 to 5 days despite IV methylprednisolone at 2 to 4 mg/kg/day, promptly start immunosuppressive therapy such
 

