**Example:**

1. Cohort dose: 75 mg

2. Dose to be added into infusion bag:

Dose (mL) = 75 mg/20 (mg/mL) = 3.8 mL

3. The theoretical number of vials required for dose preparation:

Number of vials = 3.8 (mL)/20 (mL/vial) = 1 vial

**Phase II trial of durvalumab  
(Medi4736) plus tremelimumab with  
concurrent radiotherapy in patients  
with localized muscle invasive bladder  
cancer treated with a selective bladder  
preservation approach -  
INMUNOPRESERVE STUDY -  
MANUSCRIPT 2022**

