### 2.3.2. TOXICITIES GRADE $\geq 3$

Table 203: Toxicities with grade 3 or higher

Adverse Event (CTC)	N (%)
---------------------	-------

Table 204: List of all toxicities with grade 3 or higher

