### 1.1.1. AES

### 1.1.1.1. Most frequent AES

Table 205: Most frequent AEs (related or not to treatment) (at least 3 pts approx.  $\geq 10\%$ )

	N	%	LL IC 95%	UL IC 95%
No				
Sí				
Total				
No				
Sí				
Total				

Table 206: Most frequent AEs (at least 3 pts approx.  $\geq 10\%$ ) according to grade

### 1.1.2. AES GRADE ≥ 3

Table 207: AEs with grade 3 or higher

Adverse Event (CTC)	N (%)
---------------------	-------

Table 208: List of all AEs with grade 3 or higher

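### The SAP safety shells name a non-serious Grade 1-2 adverse event term only if at least 3 of 32 patients had it, which is narrower than the table planned in protocol Table 8

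*Combined protocol and SAP*

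**What the plan says.** Protocol 11.2.2, Table 8, row Secondary 2 (safety and tolerability), plans two outputs for the safety population. The first is a "Frequency table with adverse events, grades and relationship to study drugs and to radiotherapy treatment". The second is a separate frequency table of severe toxicity. Neither carries a minimum count.

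The only SAP in the documents is a set of table shells whose title ends in "MANUSCRIPT 2022". Its safety tables are these:

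- **Table 198:** yes/no patient counts for broad categories (any serious AE, any related AE, any AE of Grade 3 or higher, and so on). No AE terms.
- **Tables 199-200:** serious AEs, by term and as a list.
- **Tables 201-202:** treatment-related events, overall and by grade. Table 201 is headed "Most frequent toxicities (at least 3 pts approx", with about 10% or more as the stated equivalent, and Table 202 has the same restriction.
- **Tables 203-204:** "Toxicities with grade 3 or higher", by term and as a list.
- **Tables 205-206:** all AEs, overall and by grade. Table 205 is headed "Most frequent AEs (related or not to treatment) (at least 3 pts approx", and Table 206 has the same restriction.
- **Tables 207-208:** all AEs of Grade 3 or higher, by term and as a list.

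**The concern.** Safety and tolerability of the combination with concurrent radiotherapy is a secondary objective (protocol 2.2). In 32 patients, a term seen once or twice is weak evidence about its true rate, so leaving it out does not show that it is rare.

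The events at issue are not always trivial. Appendix 1 generally asks for study drug to be held for a Grade 2 immune-mediated event. It also allows isolated Grade 2 hypothyroidism to be managed with replacement therapy and no interruption of study drug. An event of that second kind, reported as an AE in 1 or 2 patients, need leave no trace by term anywhere in the shells. The same holds for an outpatient Grade 2 event after the third and last dose but inside the 90-day recording window (protocol 10.3.1). A reader who later wants to pool low-grade events across small trials could not recover these from Tables 198-208.

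**Working it through.** **Inputs.** The safety set is n = 32 (SAP 3.1). The cut-off is at least 3 patients (Tables 201, 202, 205, 206). Protocol 1.4.2 says that the events reported in at least 10% of patients on the combination "are fatigue, diarrhoea, nausea, dyspnea, decreased appetite, pruritus, vomiting, anaemia, constipation, cough, abdominal pain, pyrexia, back pain, hyponatremia and rash".

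**The plan's own figure.** 3/32 = 9.4%, and 10% of 32 is 3.2, so the stated equivalence of 3 patients with about 10% is right.

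**Which terms fall through.** 1/32 = 3.1% and 2/32 = 6.3% are below the cut-off of Tables 201, 202, 205 and 206. A non-serious term is outside Tables 199-200. A Grade 1-2 term is outside Tables 203, 204, 207 and 208. Only Table 198 remains, which counts the patient but names no term and gives no grade for such an event.

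**What 1 or 2 patients can mean.** Exact (Clopper-Pearson) 95% intervals:

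- 1/32: 0.1% to 16.2%
- 2/32: 0.8% to 20.8%

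**Chance that a term occurs but is not named.** Let q be the rate of non-serious Grade 1-2 cases and r the rate of cases that are listed at any count (serious, or Grade 3 or higher). Take one grade per patient and independent patients. Then

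P = 32 q (1 − q − r)^31 + 496 q² (1 − q − r)^30, where 496 = 32 × 31 / 2.

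*Rate anchored in the documents.* With a total rate of 10% and r = 0:

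32 × 0.10 × 0.90^31 + 496 × 0.01 × 0.90^30 = 0.122 + 0.210 = 0.332.

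This is an upper bound for any total of 10% or more. For a fixed total, P is largest when r = 0, because 1 − q − r is then fixed and P rises with q. With r = 0, P peaks at 0.598 when q = 4.4% and falls beyond that. Holding the total at 10%, r = 1% gives 0.280 and r = 2% gives 0.232. At a total of 15% with r = 0, P is 0.116.

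*Assumed rates.* The documents give no rates for rarer terms, so these q values are assumptions. With r = 0:

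- q = 1%: 0.271
- q = 2%: 0.450
- q = 3%: 0.552
- q = 4.4%: 0.598 (maximum)
- q = 5%: 0.592

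*Sensitivity to r.* An added 1% rate of Grade 3 or higher cases lowers the figures at q = 1%, 3% and 5% to 0.198, 0.402 and 0.429. Hospitalisation also matters, because an event that "Requires in-patient hospitalization or prolongation of existing hospitalization" is serious by protocol 10.1.2 and would be listed. For Grade 2 pneumonitis, Appendix 1 advises: "Monitor symptoms daily and consider hospitalization". If a quarter of all Grade 1-2 cases were hospitalised (an assumption), a total Grade 1-2 rate of 1%, 3% or 5% would give 0.196, 0.381 or 0.394.

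**The case against.** **Table 8 does not promise every term.** It is silent on a display threshold, and silence is not a commitment to have none. Read narrowly, Tables 198 and 201-208 together give frequencies, grades and relationship. This stands as far as it goes: there is no contradiction. But Table 8 describes a table of AEs without qualification, beside a separate table of severe toxicity, and a table limited to the most frequent terms is narrower than that.

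**These are manuscript shells.** A frequency cut-off is ordinary in a paper, and a clinical study report could list everything. That is possible, but the documents do not show it. Protocol 10.3.5 mentions the study report for laboratory tests and vital signs, and 8.3.1.2 for further urine analyses. Protocol 14.1 says that the statistical report follows the SAP and client-specific requirements. No all-terms AE shell is in the documents.

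**Little is left over.** Serious events and those of Grade 3 or higher are listed at any count. Some Grade 2 events may surface as free-text reasons for missed or delayed doses (Tables 29, 30, 33-35), radiotherapy interruptions (Tables 37-38) or end of treatment (Table 40). This reduces the gap without closing it: those tables are not graded AE tables, and they miss events that change no treatment or that follow the last dose.

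**The cut-off is not the only cause.** Under 10.3.5, deterioration in a protocol-mandated laboratory value is reported as an AE only if it meets a serious criterion or leads to discontinuation. Low-grade laboratory-only changes would mostly be missing from AE tables with or without a cut-off. That is correct, and they are outside this point.

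**Conclusion.** The gap is real and minor. A stated display rule narrows a planned secondary safety output, and a non-serious Grade 1-2 term in 1 or 2 of 32 patients is not shown by term or grade in Tables 198-208.

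On size, only the bound of 0.33 is anchored in the documents. It assumes that the 10% floor in protocol 1.4.2 carries over to this population with radiotherapy added. The range of about 0.27 to 0.60 rests on assumed Grade 1-2 rates of 1% to 5% with no serious or Grade 3 or higher cases. All these figures are per term, and they read the cut-off as applying to a term's total count across grades. They describe how often a term lands at 1 or 2 patients, not an error in any result.

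Three stronger readings are tempting and are not supported:

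- **That the SAP breaks a protocol commitment.** Table 8 is silent on a minimum count.
- **That these events will never be reported.** A fuller output may exist outside these documents.
- **That a promised table of adverse events of special interest is missing.** Table 8 plans none, and 10.1.3 treats these events as a matter of monitoring and rapid reporting.

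The primary result, the toxicity rule for the first patients, and the serious and Grade 3 or higher listings do not depend on this point.

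**What to change.** Add one supplementary frequency table of all AE terms, by maximum grade and by relationship to durvalumab, tremelimumab and radiotherapy, with no minimum count. Keep Tables 201, 202, 205 and 206 as highlights.

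The cost is one more table shell and a longer safety output. No new data are needed. Protocol 10.3 already collects grade and causality against the investigational products for each AE, and Table 198 already has separate rows for events related to durvalumab, tremelimumab and radiotherapy. The change is cheap and worth making, but nothing else in the plan depends on it.

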### 2.3.2. TOXICITIES GRADE $\geq 3$

Table 203: Toxicities with grade 3 or higher

Adverse Event (CTC)	N (%)
---------------------	-------

Table 204: List of all toxicities with grade 3 or higher

### 1.1.1. AES

### 1.1.1.1. Most frequent AES

Table 205: Most frequent AEs (related or not to treatment) (at least 3 pts approx.  $\geq 10\%$ )

	N	%	LL IC 95%	UL IC 95%
No				
Sí				
Total				
No				
Sí				
Total				

Table 206: Most frequent AEs (at least 3 pts approx.  $\geq 10\%$ ) according to grade

### 1.1.2. AES GRADE ≥ 3

Table 207: AEs with grade 3 or higher

Adverse Event (CTC)	N (%)
---------------------	-------

Table 208: List of all AEs with grade 3 or higher
